11.0 Study Design

11.1 * Study design (Help Text updated 9/13):

We propose to test the efficacy of the Preventing Loss of Independence through Exercise (PLIÉ) program by performing a randomized, controlled trial (RCT) at adult day health centers that have current contracts with the San Francisco Veterans Affairs Medical Center (SFVA) or other local VA facilities. We propose to enroll participants in cohorts of 20 at a given center at a time and randomize them in blocks to Group 1 (n=10) or Group 2 (n=10) using a waitlist design. Veterans will be prioritized for enrollment. Study participants randomized to Group 1 will participate in the PLIÉ program at least 2 days/week, 1 hour/day for a 4-month intervention period while study participants randomized to Group 2 will engage in usual activities. After 4 months, Group 1 will 'graduate' and will be encouraged to engage in maintenance activities while Group 2 participates in PLIÉ at least 2 days/week, 1 hour/day for 4 months. Outcomes and potential mediators will be assessed in all study participants at baseline, 4 and 8 months to examine the effect of the intervention in both groups as well as maintenance of intervention effects post-intervention in Group 1. Study sites will include: Marin Adult Day Health Center in Novato, CA; Institute on Aging, San Francisco, CA; Catholic Charities, Santa Rosa, CA; and Alzheimer's Services of the East Bay, Oakland, CA. Other study sites will be added to the protocol over time.

11.2 If this is a clinical trial, check the applicable phase(s) (Help Text updated 9/13):

- Phase I
- Phase II
- Phase III
- Phase IV

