All primary analyses will be performed using intent-to-treat principles. All variables will first be assessed for evidence of outlier values or skewed distributions. Baseline characteristics and potential confounders will be summarized for participants randomized to Group 1 versus Group 2 using standard methods such as means/standard deviations and medians/inter-quartile ranges for continuous variables and frequencies with percentages for categorical variables. Differences between the groups at baseline will be statistically tested using t-tests for continuous variables or non-parametric alternatives as indicated and Chi-square tests for categorical variables. Any differences detected will be adjusted for in multivariable models. Our primary analytic approach will be mixed effects linear regression which will enable efficient estimation of treatment effects, inclusion of all study participants in intent-to-treat analyses, and the same analytic approach to be used for all three Aims. Analyses will focus on differences in outcomes when participating in PLIE vs. UC. Fixed effects terms will be included for treatment (PLIE vs. UC), sequence (Group 1 vs. Group 2), time (baseline, 4 months, 8 months) and the interaction between treatment*time. Subjects will be modeled as random effects. Models also will adjust for any baseline differences in demographic factors or confounders that may occur due to chance. Covariates will be included to adjust for any co-interventions that occur (e.g., medication changes), and sensitivity analyses will be performed excluding participants who experience co-interventions. Standard diagnostic tests will be performed to examine model assumptions and distributions of residual values and to assess for potential leverage and influence points. To minimize the risk of Type I error due to multiple comparisons with co-primary outcomes, we will adjust p-values using bootstrapping (SAS Proc Multtest).

12.4 If this study has undergone scientific or scholarly review, please indicate which entity performed the review:

- Cancer Center Protocol Review Committee (PRC) (Full approval is required prior to final CHR approval for cancer-related protocols.)
- CTSI Clinical Research Center (CRC) advisory committee
- Departmental scientific review
- Other:

Specify **Other**:

Department of Veterans Affairs; SFVA R&D Committee

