14.0 Sample Size and Eligibility

14.1 Number of subjects that will be enrolled at UCSF and affiliated institutions:

120

14.2 Total number of subjects that will be enrolled at all sites (Help Text updated 9/13):

120

14.3 Estimated number of people that you will need to consent and screen here (but not necessarily enroll) to get the needed subjects:

218

14.4 Explain how and why the number of subjects was chosen (Help Text updated 9/13):

Although our primary analytic approach will be mixed effects linear regression models using a waitlist design, sample size estimates and power calculations are based on the simpler (and more conservative) situation of a repeated measures design with 1 pre and 2 post measures using effect size estimates from our pilot study, correlation between measures of 0.75 (based on our pilot data) and estimated alpha=0.03 (to account for multiple comparisons for our three co-primary outcomes). Sample size estimates at 80% power ranged from n=12/group to n=59/group depending on the effect size. Conversely, power estimates using a sample size of 60/group ranged from 81% to 100%. Power ranged from 71% to 100% for all outcomes even with 20% attrition. We estimate that we will need to contact and screen 218 potential study participants in order to enroll our target sample of 120 based on our pilot study response rate of 55%.

Sample Size and Power Estimates	Effect Size	Sample size, 80% Power	Power, N=60/ Group	Power, 20% Attrition
Co-Primary Outcomes				
Cognitive function (ADAS-cog)	0.76	12	1.00	1.00
Physical performance (SPPB)	0.34	59	0.81	0.71
Quality of life (QOL-AD)	0.83	10	1.00	1.00
Secondary Outcomes				
Caregiver burden (CBI)	0.49	29	0.97	0.92

14.5 * Eligible age range(s):

- 0-6 years
- 7-12 years
- 13-17 years
- 18+ years

14.6 Inclusion criteria:

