We propose to enroll 120 dyads of individuals with dementia and their primary caregivers, with a goal of 20 dyads per intervention site. Veterans with dementia who are current clients at the site will be prioritized for enrollment. If we are unable to enroll our target sample of 20 Veterans with dementia at a given site, enrollment will be opened to non-Veterans with dementia at the site as well as Veterans and non-Veterans with dementia who are not currently clients at the site but are living in the community near the site and willing to attend for the study. Caregivers are not required to be Veterans, but their participation is necessary because they are providing care to the primary participants, many of whom will be Veterans.

Inclusion criteria, primary participant:

- diagnosis of memory loss or dementia
- mild to moderate severity (defined as Clinical Dementia Rating of 0.5, 1, or 2)
- English language fluency
- attendance or willingness to attend adult day health center at least 2 days/week on days that PLIE will be offered

Inclusion criteria, caregivers:

- Provide care for primary participant
- Able to answer study questionnaires related to participant's functional status, dementia-related behaviors, quality of life and their own feelings about caregiving
- English language fluency

14.7 Exclusion criteria:

Exclusion criteria, primary participant:

- Plans to change days of attendance during the study period so that participant would no longer be attending on at least 2 PLIE days/week
- Planning to leave the facility during the study period and not willing to come for PLIE classes at least 2 days/week
- Severe vision or hearing impairment (e.g., unable to see or hear well enough to follow instructions)
- Several physical impairment (e.g., paralysis or hemi-paralysis; wheel-chair or bed bound)
- Severe mental health condition (e.g., uncontrolled depression, PTSD, bipolar disorder)
- Limited life expectancy (e.g., enrolled in or eligible for hospice; metastatic cancer)
- Started dementia medication (cholinesterase inhibitor or memantine) in past 3 months
- Planning to change dementia medication during the study period
- Current participation in another research study
- Lack of legal supporting documentation for HIPAA (e.g., durable power of attorney, court ordered legal guardianship, advance health directives), If determined to lack capacity to consent.
- Lack of consent/assent to study procedures

Exclusion criteria, caregivers:

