Randomization. Study participants will be enrolled in one study site at a time in blocks of 20, and the randomization sequence will be generated in advance in blocks of 20 (10 Group 1, 10 Group 2) using a random number generator on a computer. The sequence will be stored in a secure location accessible only to intervention staff, and research staff who enroll study participants and collect outcome data will be unaware of the randomization sequence.

Blinding. Because we are using a waitlist design with usual care as the control condition, it will not be possible to blind study participants or their caregivers. However, research staff who collect outcome data will be blinded to group assignment. Every effort will be made to ensure that blinding is maintained including: 1) having interviewers remind study caregivers not to discuss any aspect of the study or ask any questions related to the study prior to scheduling or performing assessments; 2) excluding interviewers from staff meetings that discuss details of the intervention; and 3) maintaining the group assignment list separately from other study documentation. Interviewers also will be asked to guess which group participants were in to assess the adequacy of the blinding procedures.

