Goals Assessment. Prior to beginning the PLIÉ program, exercise instructors will meet individually with study participants and caregivers to discuss their personal goals and interests. Goals may range from concrete objectives (reaching down to tie shoes) to more general objectives (remembering appointments). Prior studies have found that rehabilitation tends to have better outcomes when patients are involved with setting their own goals. Exercise instructors will also ask about hobbies and interests of study participants as well as potential barriers and facilitators to engaging in a group exercise program. Information gathered will be used in the class setting to help tailor exercises to address individual goals and interests and to

imbue exercises with greater meaning (e.g., this exercise may help you reach down to tie your shoes; being more aware of your body and the things around you may help you remember upcoming appointments).

Usual Care (UC) Control. Those participants attending the adult day program will participate in usual activities at the center, while those from the community will continue to engage in usual activities at home. All adult day programs include some type of group physical activity (usually seated) or individualized physical therapy. Whenever feasible, we will strive to offer PLIE classes at the same time as usual exercises at the center. We will document usual care activities by collecting monthly activity schedules from study sites and by asking caregivers about usual activities over the past month during check-ins to assess for potential co-interventions or contamination. This will enable us to perform exploratory analyses to assess the effects of different usual care activities on study outcomes.

Follow-Up Assessments (participants and caregivers separately). Follow-up assessments will be performed at 4 months and 8 months for all study participants. Procedures and measures will be identical to those at baseline.

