Adherence, Adverse Events and Co-Interventions. Adherence will be monitored using class attendance logs. Adverse events will be assessed by calling caregivers on a monthly basis using a standardized questionnaire. Caregivers will be asked to report changes to the participant's health status since the last contact, including any emergency room visits, hospitalizations, or injuries. For any symptoms or events reported, caregivers will be asked if they occurred during or shortly after participating in PLIE or usual activities. Events that are serious and unexpected will be reported to an independent Data Monitoring Committee (DMC) and the IRB within 5 working days. The DMC also will review the adverse event log on a biennial basis. Based on consultations with the SFVA Research Office, adverse events that are possibly, probably or definitely study-related that occur in SFVA patients will be entered as notes into the medical record. Co-interventions also will be assessed during monthly caregiver check-ins using a standardized questionnaire that asks about any changes since last contact that might affect study outcomes including changes in medications, caregivers, medical conditions, usual activities or other factors.

Video-recording. Some of the exercise classes or assessments will be video-recorded for quality control, research or educational purposes. Everyone must consent to the video-recording for quality control and training purposes. The participants will have the option to allow for (1) private viewing only – viewing limited to the research team, auditors, and monitoring committee, or (2) private and public viewing – viewing available to the public as videos will be included in the training manual, shown at research or educational meetings, and/or posted on the study website.

Participant options for video recording will be tracked together with the main consent; i.e., that tracking will be included in the current study database. More specifically, the database includes a Consent section, under which the main consent, video recording options, and future contact consent options will be entered. This will ensure that the research team are kept informed of participant choices for video recording. Participants may be contacted after study ends regarding information about the optional participation in ongoing community classes, Participants will be sent birthday cards, and--in case of death or hospitalization--sympathy cards.

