PIs are permitted to sending annual research progress reports to funding agencies and research colleagues.

Other contact with study participants. To maintain good relationships with study participants, we may send birthday cards, get well cards and sympathy cards using IRB-approved templates. In addition, we may send periodic research progress updates using IRB-approved letters.

Implementation activities. We have received additional support from the Department of Veterans Affairs through the VA Innovators program to begin implementing PLIE as a new clinical program within VHA. To facilitate this process, we will be interviewing key VA stakeholders, patients, caregivers and clinicians regarding optimal implementation strategies; analyzing interviews to identify key themes; creating a 3-minute video 'pitch'; and drafting an implementation plan. In addition, we may offer PLIE classes at the Community Living Center, adult day programs that contract with VHA and through the YMCAs. This is considered a quality improvement project. However, some prior PLIE participants who are Veterans may be involved.

Additional measures to assess impact of North Bay fires: For caregiver participants at the Primrose site only, the Perceived Stress Scale will be administered at the mid-point and final assessments to measure the impact of the North Bay fires on general stress levels. In addition, an open-ended questionnaire will ask about the perceived impact of the fires on key study outcomes. A cover letter will inform caregivers that two new questionnaires have been added and will remind them that all study procedures are optional.

If you have a procedure table, attach it to the submission with your other study documents.

16.2 Interviews, questionnaires, and/or surveys will be administered or focus groups will be conducted:

Yes No

List any standard instruments used for this study:

Alzheimer's Disease Assessment Scale – Cognitive Subscale (ADAS-cog)
Short Physical Performance Battery (SPPB)
Quality of Life Scale in Alzheimer's Disease (QOL-AD)
Near-Infrared Spectroscopy (NIRS)
Caregiver Burden Inventory (CBI)
Disability Assessment for Dementia (DAD)
Neuropsychiatric Inventory (NPI)
Falls Efficacy Scale (FES)
Positive Aspects of Caregiving (PAC)
Geriatric Depression Scale - Short Form (GDS)
Perceived Stress Scale (Primrose caregiver participants only, Visits 2 and 3)

Attach any non-standard instruments at the end of the application.

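### The primary model omits the site cohorts used as randomisation blocks; taken alone, apart from correlation within PLIÉ classes, this leaves standard errors correct or too wide and forgoes a little power, mainly for SPPB

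*Combined protocol and SAP*

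**What the plan says.** Section 11.1 plans to "enroll participants in cohorts of 20 at a given center at a time and randomize them in blocks to Group 1 (n=10", with the other ten going to Group 2. Section 16.1 (Randomization) adds that recruitment runs one site at a time and that "the randomization sequence will be generated in advance in blocks of 20 (10 Group 1, 10 Group 2" each. Section 14.6 sets 120 dyads "with a goal of 20 dyads per intervention site", so six cohorts are expected. The site cohort is therefore the randomisation block.

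Section 12.3 lists four fixed effects (treatment, sequence, time, treatment-by-time) and then: "Subjects will be modeled as random effects". No section adds a site or cohort term. The rule that detected baseline differences between groups will be adjusted for would not bring cohort in, because cohort is balanced between groups by design.

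Section 14.4 bases power on an individual-level repeated-measures design with no site, block or class variance. SPPB is the weakest co-primary at 81% with 60 per group: "Power ranged from 71% to 100% for all outcomes even with 20% attrition", and the lower end of that range is SPPB.

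PLIÉ is taught in groups: at most five participants per instructor (Section 16.1, Intervention), or ten with two instructors (Sections 16.8 and 17.2).

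**The concern.** An analysis normally reflects the blocks used to randomise. Here the part that matters is not the average level of a site but how a site moves over time. If everyone at one centre shifts between visits, both groups of that cohort shift together. The shift drops out of the Group 1 versus Group 2 comparison, but without a cohort-by-visit term it is counted as noise.

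The documents make such movement possible. Sites run one after another, and after regional fires a measure was added at one site: "For caregiver participants at the Primrose site only, the Perceived Stress Scale will be administered at the mid-point and final assessments". What is at stake is efficiency for SPPB, the co-primary with the least power to spare.

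**Working it through.** **Reproducing the plan's figure.** Inputs from Section 14.4: SPPB effect 0.34 SD, correlation 0.75, alpha 0.03 (taken as two-sided, which reproduces the table), one baseline and two follow-up measures.

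- Variance factor = 1 + (1 + 0.75)/2 − 2(0.75) = 0.375.
- n per group = 2(0.375)(2.170 + 0.842)²/0.34² = 58.8, so 59 (stated 59).
- Power = 0.808 at 60 per group and 0.709 at 48 per group (stated 0.81 and 0.71).

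**Set-up for the check.** Total SD 1 and correlation 0.75 give a within-subject residual variance of 0.25. There are six cohorts of 10 + 10, with complete data. The contrast is the group difference in change from baseline to month 4, with Group 1 at month 8 coded as usual care.

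- SE = √(4 × 0.25/60) = 0.129. Power for 0.34 SD is 67.4%. This is below 81% only because the contrast uses one follow-up visit instead of two.
- Within-subject df = 120 × 3 − 120 − 4 = 236. Cohort-by-visit terms take 5 × 2 = 10, leaving 226.

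**Stable site differences.** These lie wholly in the subject intercept. In a simulated data set fitted with and without a site main effect, the SE of the contrast was 0.1437 both times.

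**Site-by-visit variation.** Let r be the site-by-visit variance as a share of the residual variance (assumed; none is given in the documents).

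- Planned model: residual sum of squares = 0.25·χ²(226) + 0.25(1 + 20r)·χ²(10), so the expected residual variance is inflated by 1 + 200r/236.
- With block terms: 0.25·χ²(226).
- The contrast itself does not contain r.

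Results by simulated draws (Monte Carlo error at most 0.0005), with r either added to the residual of 0.25 or taken out of a fixed total of 0.25:

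| r | Residual inflation | Type I error, planned | SPPB power, added: planned / block | SPPB power, total held: planned / block | Forgone |
|---|---|---|---|---|---|
| 0 | 1.000 | 0.030 | 67 / 67% | 67 / 67% | 0 |
| 2% | 1.017 | 0.029 | 67 / 67% | 68 / 68% | about 0.6 points |
| 5% | 1.042 | 0.027 | 66 / 67% | 68 / 70% | about 1.7 |
| 10% | 1.085 | 0.024 | 64 / 67% | 69 / 72% | about 3 |
| 20% | 1.169 | 0.019 | 61 / 67% | 70 / 76% | about 6 |

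The last column uses unrounded values. With block terms, type I error is 0.030 throughout. For caregiver burden (effect 0.49, r added) power is 94.6, 93.5 and 92.3% at r = 0, 10 and 20%, against 94.6% with block terms. ADAS-cog and QOL-AD stay near 100%.

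**Scale.** If one cohort of six shifts by d SD at months 4 and 8, the inflation is 1 + [20(5/6)(2/3)d²/0.25]/236. The 10% case corresponds to d = 0.67, or 0.67 × 2.4 = 1.6 SPPB points using the pilot SD in Section 13.2. A shift of 0.34 SD, the size of the treatment effect, inflates the residual variance by only about 2%.

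**Dependence on the contrast.** If Group 1 at month 8 is coded as PLIÉ, SPPB power at r = 0, 10 and 20% is 80, 78 and 75% planned against 80% with block terms. If the effect is averaged over months 4 and 8 with no carryover, it is 99.8% planned against 99.9% with block terms even at 20%.

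**Class correlation.** Simulated type I error with r = 10% and class ICC 0.02, 0.05 and 0.10 (assumed, on change scores):

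| Class size | Planned model | With block terms |
|---|---|---|
| 10 | 0.031 / 0.041 / 0.062 | 0.039 / 0.052 / 0.077 |
| 5 | 0.027 / 0.032 / 0.040 | 0.033 / 0.040 / 0.050 |

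**The case against.** The strongest objection is that the remedy could make the confirmatory test more liberal. Group teaching is documented, whereas site-by-visit variance in SPPB is not, and the class figures show block terms raising type I error if class correlation exists. This stands as a cost to be stated. It is not a reason to leave the blocks out: the excess error comes from class clustering, which the plan also ignores, and an accidental offset of unknown size is no safeguard.

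Three further objections also stand and limit the point.

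- **Size.** At shares of 2 to 5% the gain is only about 0.6 to 1.7 points; the 10% case needs a large shift of a whole cohort.
- **Evidence.** The fire-related measures concern caregiver stress at one site and report nothing about physical performance.
- **Partial handling.** Section 16.1 collects monthly site activity schedules and caregiver reports, and Section 12.3 adjusts for co-interventions, which may capture some site-specific change.

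A reader might infer more than the documents support:

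- *That ignoring the blocks inflates type I error.* It does not; balanced block variation that is ignored widens standard errors or leaves them unchanged.
- *That the planned standard errors are therefore safe.* They are not in general; shared PLIÉ classes can make them too narrow.
- *That SPPB power falls below the stated 81% or 71%.* Those figures assume no site term. If the total variance is what the plan assumed, planned-model power does not fall; it is only lower than a block-adjusted analysis would give.

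**Conclusion.** The point holds as a minor efficiency improvement. The block omission, taken alone, makes the test nominal or conservative and forgoes about 0.6 to 6 points of SPPB power at assumed site-by-visit shares of 2 to 20%, and nothing at zero. The size of the gap is about the same whether that variance is added to the residual or taken from a fixed total, but it changes with the coding of Group 1 at month 8 and with the treatment contrast tested.

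The direction is firm for balanced data without class correlation. The size rests on variances that the documents do not give, on the plan's correlation of 0.75, and on a baseline-to-month-4 contrast. In simulation with 20% random loss after baseline the pattern is the same: SPPB power 57, 54 and 51% planned at shares of 0, 10 and 20%, against 57% with block terms.

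**What to change.** Add site-cohort and site-cohort-by-visit fixed effects to the primary model in Section 12.3, for participant and caregiver outcomes. A site main effect alone would not help.

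Cost: SAP wording and 5 + 10 = 15 parameters. The critical value moves from 2.183 to 2.184. With no site-by-visit variance, SPPB power is unchanged at 67.4%, or goes from 57.4% to 57.0% with 20% attrition.

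Alongside this, prespecify a sensitivity analysis for participant outcomes with a class-level random effect in PLIÉ periods and small-sample degrees of freedom. Section 16.1 supplies the data: "Adherence will be monitored using class attendance logs". Give a rule for participants who attend more than one class. State its limits:

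- There are only about twelve classes over both periods if classes hold ten. Simulated SPPB power is about 46–56, 44–52 and 34–39% at class ICC 0.02, 0.05 and 0.10, so the analysis is imprecise and should stay secondary.
- It treats usual-care participants as unclustered, although "All adult day programs include some type of group physical activity (usually seated) or individualized physical therapy".

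How Group 1 at month 8 is coded needs its own statement in the SAP and is a separate point.
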